3.1 Study Objectives

3.1.1 Primary Objectives

Immunogenicity

To demonstrate non-inferiority in the immunogenicity of the liquid formulation of ROTAVIN in comparison to currently licensed frozen formulation of the Vaccine (ROTAVIN-M1®), 28 days after

the last dose of the vaccine when administered to infants in a two-dose schedule starting at 60-91 days of age.

Safety

To evaluate the safety of liquid formulation of ROTAVIN in comparison with currently licensed frozen formulation (ROTAVIN-M1[®]), in terms of solicited reactions after each dose of vaccine.

3.1.2 Secondary Objectives

Immunogenicity

To further characterize the immunogenicity of the liquid formulation of ROTAVIN in comparison with currently licensed frozen formulation of the vaccine (ROTAVIN-M1[®]).

Safety

To evaluate the safety of the liquid formulation of ROTAVIN in terms of immediate post-vaccination events, unsolicited adverse events and serious adverse events, including monitoring for intussusception

3.2 Study Endpoints

3.2.1 Primary Endpoints

Immunogenicity

Rotavirus vaccine immunogenicity will be tested on serum samples obtained in a subset of 450 participants before the first vaccination and four weeks after the second vaccination using a validated ELISA assay. The primary immunogenicity endpoint is as follows:

- Geometric mean concentration (GMC) of serum anti-rotavirus IgA antibody concentrations 28 days after the second vaccination.

Safety

Solicited post-vaccination reactogenicity (fever, diarrhea, vomiting, decreased appetite, irritability, and decreased activity level) during the 7 day period (Day 1-7) after each vaccination.

3.2.2 Secondary Endpoints

Immunogenicity

- Percentage of participants with seroconversion in serum anti-rotavirus IgA antibody concentrations 28 days after the second vaccination defined as follows:
 - For participants with a negative pre-vaccination IgA concentration (< 20 IU/ml), a positive post-vaccination IgA concentration (≥ 20 IU/ml);
 - For participants with a positive pre-vaccination IgA concentration, a post-vaccination IgA concentration at least 4 times as high as the pre-vaccination IgA concentration.
- Percentage of participants with seropositivity at baseline and 28 days after the second vaccination. Seropositivity is defined as serum IgA antibody concentration ≥ 20 IU/ml.

Safety

- Immediate adverse events, within 30 minutes after each vaccination.
- Unsolicited AEs from vaccination through four weeks after each dose.
- Serious adverse events (SAEs) and intussusception from first vaccination through four weeks after the last vaccination.

4. Investigational Plan

4.1 Overall Study Design and Plan

The study is designed as a phase III, multicenter, randomized, partially double-blinded, active controlled study enrolling 825 infants 60-91 days of age. The objective of the study is to compare the safety and immunogenicity of the liquid formulation of ROTAVIN with already licensed vaccine ROTAVIN-M1®.

The study will be conducted at commune health centers in Nam Dinh and Quang Ninh provinces in Vietnam. Prospective participants, whose parent or legal guardian sign an informed consent form will be assessed for eligibility to participate in the study. Screening for eligibility will include solicitation of medical history, assessment of vital signs and physical examination. If the participant is found to be eligible, the infants will be allocated to one of the two groups at a ratio of 2:1 to receive the study vaccine with 550 participants receiving the liquid formulation of ROTAVIN and 275 participants receiving the frozen formulation (ROTAVIN-M1®). The study will be conducted according to a partially blinded study design in which the vaccine administrator will be considered unblinded whereas the parents, and rest of the study team including endpoint assessor will be blinded to the treatment received by the child. Two doses of vaccine will be administered 8 (+2) weeks apart (minimum interval of 8 weeks and maximum of 10 weeks), with the first administration given at 60-91 days of age (both days inclusive). Childhood vaccines as per the Expanded Program for Immunization (EPI) of the Government of Vietnam will not be allowed within 7 days before or after study vaccine administration.

To evaluate the Rotavirus vaccine immunogenicity, blood samples will be obtained from all the participating infants from Quang Ninh site before the first vaccination and four (+2) weeks after the second vaccination. Immunogenicity will be assessed in all infants who provided blood samples at the selected site. Serum Anti-rotavirus IgA antibodies will be analyzed at Cincinnati Children's Hospital Medical Center (CCHMC), Cincinnati, Ohio, USA using a validated ELISA which uses strain 89-12 as a substrate.

Vaccinated participants will be observed for immediate adverse events for 30 minutes after each vaccination. Active surveillance for vaccine reactogenicity (solicited reactions) over the 7-day period after each vaccination, unsolicited AEs for 4 weeks after each vaccination and SAEs including intussusception over the period between first vaccination and four weeks after the last vaccination will be conducted for all infants.

This study will have extensive safety monitoring in place. At the performing site level, the study site investigators and their clinical staff will be responsible for continuous close safety monitoring of all study participants and for alerting the protocol team if unexpected concerns arise. A team of vaccine experts, Safety Review Committee (SRC) composed of a group of physicians, which include but not limit to the designated investigator from study team and the Medical Officer(s)

from POLYVAC and PATH, a Pharmacovigilance/Medical officer from the CRO and an independent vaccine expert will be closely following the study for safety oversight. The SRC may seek independent expert medical opinion as dictated by the occurrence of certain events.

The SRC will have provision of expedited meeting that could be triggered by reporting of predefined AEs. The SRC may also seek independent expert medical opinion as dictated by the occurrence of certain events.

The schedule of study assessments is given in Table A1 below.

Table A1: Trial Schema- Schedule of Events

Visit	V1*		V2*	V3
Time point (Day)	D1		D57	D85
Interval (window period)	Screening	Post enrollment	V1+ 8 (+2) weeks	V2+ 4 (+2) weeks
Information process and written informed consent	X			
Collect baseline demographic data	X			
Collect/review medical history	X			
Perform Physical examination and Vital examination	X ^a		X	X
Check inclusion/exclusion criteria	X			
Enrollment	X			
Randomization		X		
Collect blood for immunogenicity assessment ^b		X (Pre-dose)		X
Check withdrawal criteria			X	X
Check contraindications, warnings and precautions to vaccine administration			X	
Study vaccination		X	X	
Observe for immediate reactions for 30 minutes		X	X	
Perform post-vaccination Vital examination and targeted physical examination if required.		X	X	
Issue and instruct parent/LAR of participant on use of diary card		X	X	
Record solicited AEs within 7 days post vaccination		X	X	
Safety follow-up by health worker ^c		X	X	
Record unsolicited AEs, including SAEs		X	X	X
Record any concomitant medications/vaccinations		X	X	X
Review interim medical history and record any intercurrent medical conditions			X	X
Participant completion of study				X

D = day; AE = adverse events; SAE = serious adverse event; Shading represents days of vaccination; V=Visit number.

* The study visits will be planned in advance such that the EPI vaccination days fall either more than 7 days before or after the study vaccination day. This will allow the participant to receive EPI vaccines in the window allowed by the protocol.

^a Symptom based physical examination to be performed if screening is being repeated and there is any change in health since last screening.

^b At Quang Ninh site

^c This includes visit by the health worker to the participant's home on Day 2/58 (+1) and 8/64 (+2) after each vaccination and a telephone call on Day 5/61 (+2).

4.2 Selection of Study Population

Approximately 825 healthy male and female infants, 60-91 days of age will be enrolled in the study from the two provinces in Vietnam.

Participant Inclusion Criteria

The following criteria must be met before a participant may be enrolled for participation:

1. Healthy infants as established by medical history and clinical examination before entering the study.
2. Age: 60-91 days (both days inclusive) at the time of enrollment.
3. Parental/Legally Acceptable Representative (LAR) ability and willingness to provide written informed consent.
4. Parent/LAR who intends to remain in the area with the child during the study period.

Participant Inclusion Criteria

Participants meeting any of the temporary exclusion criteria can be rescreened for eligibility at a later time and enrolled if eligible at that time.

Participants meeting any of the following criteria will be excluded from participation:

1. Presence of diarrhea or vomiting in the previous 72 hours or on the day of enrollment (temporary exclusion).
2. Presence of fever on the day of enrollment (temporary exclusion).
3. Acute disease at the time of enrollment (temporary exclusion).
4. Concurrent participation in another clinical trial at any point throughout the entire timeframe for this study.
5. Presence of significant malnutrition (weight-for-height z-score < -3SD median).
6. Presence of any systemic disorder (cardiovascular, pulmonary, hepatic, renal, gastrointestinal, hematological, endocrine, immunological, dermatological, neurological, cancer, or autoimmune disease) as determined by medical history and / or physical examination which would compromise the participant's health or is likely to result in nonconformance to the protocol.
7. History of congenital abdominal disorders, intussusception, or abdominal surgery.
8. Known or suspected impairment of immunological function based on medical history and physical examination.
9. Household contact with an immunosuppressed individual or pregnant woman.
10. Prior receipt of rotavirus or an intent to receive this vaccine from outside of the study center during study participation.
11. Prior receipt of EPI vaccination during past 7 days or plan to receive them within next 7 days.

12. A known sensitivity or allergy to any components of the study vaccine.
13. History of allergy to antibiotic kanamycin.
14. Clinically detectable significant congenital or genetic defect.
15. History of persistent diarrhea (defined as diarrhea that lasts 14 days or longer).
16. Receipt of immunoglobulin therapy and / or blood products since birth or planned administration during the study period.
17. History of chronic administration (defined as more than 14 days) of immunosuppressants including corticosteroids. Infants on inhaled or topical steroids may be permitted to participate in the study.
18. Any medical condition in the parent/LAR or infant which, in the judgment of the Investigator, would interfere with or serves as a contraindication to protocol adherence.

4.3 Treatment

4.3.1 Treatments Administered

The treatments administered are:

1. **Test Vaccine – ROTAVIN liquid formulation:** This is a live attenuated human rotavirus vaccine (rotavirus strain G1P[8]) at a dosage of $\geq 2 \times 10^6$ plaque focus units (PFU) / dose of 2 ml. The vaccine can be stored and transported at 2-8°C. The vaccine is for oral use. ROTAVIN liquid formulation has a sterile, yellow, clear liquid, free of visible particles, to be used after shaking well.
2. **Comparator Vaccine – ROTAVIN-M1®:** Live Attenuated human rotavirus vaccine (rotavirus strain G1P[8]) at a dosage of $\geq 2 \times 10^6$ plaque focus units (PFU) / dose of 2 ml. The vaccine is for oral use. ROTAVIN liquid formulation has a sterile, pink clear liquid, free of visible particles, to be used after shaking well.

This frozen vaccine vial will be stored at -20°C. The vaccine can also be stored and transported at 2-8°C up to 2 months. For this study ROTAVIN-M1® will be supplied monthly by the manufacturer with storage and transport at 2-8°C at the site.

4.3.2 Method of Assigning Participants to Vaccine groups (Randomization)

The study will be conducted in the Nam Dinh and Quang Ninh provinces in Vietnam. Randomization and all study related activities will take place at approximately 12 commune health centers associated with one of the sites, and not at the sites. Within each site, the commune health centers will be divided into two independent teams, Team 1 and Team 2.

A manual randomization process will be used. Randomization will be stratified by site and team using a permuted block design. The unblinded team at the CRO will create two sealed opaque envelopes for each participant. When an infant is randomized, the seal of the envelope infant's participant ID is broken, and the vaccine with the code given inside the envelope is administered to the participant by the unblinded vaccine administrator. After vaccination, the envelope will be resealed and sent back to the site for data entry. The unblinded site staff will re-open the envelope

to enter the data into Advantage eClinicalSM. After data entry, the envelope will be resealed and kept in a secure locker at the site.

4.3.3 Blinding

The study will be conducted according to a partially blinded study design since the colour of the two vaccines is different. With the exception of the designated unblinded site personnel described below, all study site personnel, the PI, PATH, POLYVAC and the CROs (except the unblinded team at the CROs), will remain blinded to participants' treatment assignments until final database lock and study unblinding. Those who perform the clinical evaluations (such as but not limited to assessment of medical history, vital signs assessment, and PE), will be blinded with respect to the identity of the vaccine administered to the participants. The parents will also remain blinded to the treatment received by the child, throughout the study duration.

The randomization list for participants will be developed by an independent statistician and will be used by an unblinded team at POLYVAC to label study vaccine vials and then it will be immediately sealed. During conduct of the study, a limited number of unblinded site personnel will be responsible for preparing and administering study vaccines, performing vaccine accountability, and maintaining the security of the randomization list. The unblinded site personnel will not be involved in the safety assessment of the participants or in any other aspect of the study.

If any participant experiences an SAE possibly related to receipt of study treatment, treatment allocation to the participant may be communicated to the investigator only if that information is deemed necessary to properly treat the participant for the SAE. Written procedures for blinding, storage, and opening of study codes, in compliance with the approved protocol, will be developed to ensure the study is not unnecessarily unblinded.

4.3.4 Concomitant Medications/Treatment

Childhood vaccines as per the EPI of the Government of Vietnam [Diphtheria, Tetanus, Pertussis, Haemophilus influenzae type B and Hepatitis B vaccine (DTwPHib-HepB) and Oral Polio Vaccine (OPV)] and Pneumococcal vaccines will be allowed during the study period, but they should not be administered within 7 days before or after study vaccine administration. This is required to avoid any overlap of safety event due to study vaccine and EPI vaccines. The study participants may receive additional doses of OPV as required during special immunization rounds irrespective of the timing of study vaccine.

5. Sample Size Considerations

The sample size for the study was determined based on the regulatory requirement to submit safety data for 500 vaccine recipients receiving the new vaccine. Considering a dropout rate of 10% the study will enroll 825 infants receiving vaccines at the ratio of 2:1 (550 participants receiving the liquid formulation of ROTAVIN and 275 participants receiving the frozen formulation ROTAVIN-M1[®]).

Immunogenicity will be assessed in participants enrolled from Quang Ninh site. It is anticipated that at least 375 infants (250 ROTAVIN recipients and 125 ROTAVIN-M1[®] recipients) will provide evaluable blood samples. Considering a non-evaluability rate of approximately 15%, at least 450 participants will be enrolled at this site.

Power to show that the ratio of the GMC in the liquid formulation is ROTAVIN group to that in the ROTAVIN-M1® group is at least 0.5 was calculated using a one-sided two-sample t-test with a significance level of 0.025. With 250 evaluable participants in the liquid formulation group and 125 evaluable participants in ROTAVIN-M1® group and an assumed SD of the log10 IgA antibody concentrations of 0.8 which was estimated from a phase 3 clinical trial for ROTAVIND-M1 conducted in Vietnam, we will have 93% power to demonstrate the non-inferiority of ROTAVIN liquid formulation to ROTAVIN-M1® in terms of GMC using a one-sided two-sample t-test with a non-inferiority margin of 0.5 and a significance level of 0.025.

With the proposed sample size of 550 participants receiving the liquid formulation of ROTAVIN, this study is designed to have 95% power to detect at least one solicited post-vaccination reaction after each vaccination if true incidence is 0.55%.

With 550 vaccinated participants in ROTAVIN liquid formulation group and 275 vaccinated participants in ROTAVIN-M1® group, the study has 90% power to detect at least a 6.8% difference in percentage of participants with solicited post-vaccination reaction between the ROTAVIN liquid formulation and ROTAVIN-M1® groups after each vaccination, assuming that the rate of the solicited reactogenicity is 5% in the ROTAVIN-M1® group and a significance level of 0.05. Interim Analyses and DSMB Safety Reviews

There are no planned interim analyses or DSMB safety reviews. The SRC will meet monthly to review the blinded data to discuss any safety concerns.

6. General Statistical Considerations

7.1 Analysis Populations

Definitions of analysis populations used are:

Enrolled Population: The enrolled population is defined as all screened participants who provide informed consent and are eligible for study participation, regardless of the participant's randomization and treatment status in the study.

Full Analysis (FA) population: The full analysis population is defined as all participants in the enrolled population who were randomized, received the first dose of the study vaccination, and provided at least one evaluable serum sample. The analysis based on this population will serve as supportive results for all immunogenicity objectives.

Participants in the FA population will be analyzed "as randomized", i.e. according to the vaccine a participant was designated to receive, which may be different from the vaccine that the participant actually received.

Per Protocol (PP) population: The per-protocol population is defined as all participants in the FA population who correctly received both study vaccines per randomization with no major protocol deviations that are determined to potentially interfere with the immunogenicity assessment of the study vaccines. This population will serve as the primary analysis population for all immunogenicity objectives. The criteria for exclusion of participants from the PP population is described in Section 10, Table A2, of this SAP.

Safety population: The safety population is defined as all participants in the enrolled population who received at least one dose of study vaccination and had any safety data available.

Participants in the safety population will be analyzed as “treated”, i.e. according to the actual vaccine received at the first dose. All safety analyses will be performed using this population. The denominators for different safety endpoints may vary according to the number of participants with available data for the specific endpoint. For instance, the solicited adverse event endpoints will be based only on those who have the corresponding CRF data regardless of other safety follow-up data.

The immunogenicity primary and secondary endpoints will be performed on the PP and FA population. Safety primary and secondary endpoints will be performed on the safety population. All other baseline and safety analyses, unless stated otherwise, will be performed on the safety population.

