12.3.4 Safety population

The safety population is defined as all participants in the enrolled population who received a study vaccination and had any safety data available. Participants in the safety population will be analyzed as "treated", i.e. according to the actual vaccine received at the first dose. All safety analyses will be performed using this population. The denominators for different safety endpoints may vary according to the number of participants with available data for the specific endpoint. For instance, the solicited systemic adverse event endpoints will be based only on those who have the corresponding CRF data regardless of other safety follow-up data.

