10.	Did not meet I-E criteria but randomized	Participant met exclusion criterion	Participant met exclusion criterion 6: Any systemic disorder cardiovascular, pulmonary, hepatic, renal, gastrointestinal, hematological, endocrine, immunological, dermatological, neurological, cancer or autoimmune disease) as determined by medical history and/or physical examination which would compromise the child's health or is likely to result in non-conformance to the protocol.	PD review	Decision will be taken on the case by case basis during the review of final protocol deviation listing performed prior to database lock
11.	Did not meet I-E criteria but randomized	Participant met exclusion criterion	Participant met exclusion criterion 7: History of congenital abdominal disorders, intussusception, abdominal surgery	No PD review	Include
12.	Did not meet I-E criteria but randomized	Participant met exclusion criterion	Participant met exclusion criterion 8: Known or suspected impairment of immunological function based on medical history and physical examination.	No PD review	Exclude
13.	Did not meet I-E criteria	Participant met exclusion criterion	Participant met exclusion criterion	No PD review	Include

N	Protocol Deviation Category	Protocol Deviation Subcategory	Detailed Exclusion Description	PD Assessment	Decision for Per Protocol Population
	but randomized		9: Household contact with an immunosuppressed individual or pregnant woman.		
14.	Did not meet I-E criteria but randomized	Participant met exclusion criterion	Participant met exclusion criterion 10: Prior receipt of rotavirus or an intent to receive this vaccine from outside of the study center during study participation.	No PD review	Exclude
15.	Did not meet I-E criteria but randomized	Participant met exclusion criterion	Participant met exclusion criterion 11: Prior receipt of EPI vaccination during past 7 days or plan to receive them within next 7 days.	No PD review	Include
16.	Did not meet I-E criteria but randomized	Participant met exclusion criterion	Participant met exclusion criterion 12: A known sensitivity or allergy to any components of the study vaccine.	No PD review	Include
17.	Did not meet I-E criteria but randomized	Participant met exclusion criterion	Participant met exclusion criterion 13: History of allergy to antibiotic kanamycin.	No PD review	Include

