Yes	x (x)	x (x)	x (x)
No	x (x)	x (x)	x (x)
Pregnancy in any family member living in the same household	x (x)	x (x)	x (x)
Yes	x (x)	x (x)	x (x)
No	x (x)	x (x)	x (x)

N=Total number of participants in the safety population
x=Number of participants with an event
Percentages are based on the total number of participants in the safety population.

Table 6: Protocol Deviations by Category – Safety Population

Protocol Deviation Category	ROTAVIN N=XX x (%), E	ROTAVIN-M1 N=XX x (%), E	Total N=XX x (%), E
Total	x (%), E	x (%), E	x (%), E
Incomplete vaccination: Subject declined further vaccination but safety follow up continued	x (%), E	x (%), E	x (%), E
Incorrect Informed consent process	x (%), E	x (%), E	x (%), E
Incorrect Procedure	x (%), E	x (%), E	x (%), E
Missed Procedures	x (%), E	x (%), E	x (%), E
Subject confidentiality compromised: Personal data of subject transmitted to unintended recipient/s	x (%), E	x (%), E	x (%), E
Temperature excursion	x (%), E	x (%), E	x (%), E
Visit Window Deviation: Post vaccination assessment done before protocol specified timeline	x (%), E	x (%), E	x (%), E
Other	x (%), E	x (%), E	x (%), E

N=Total number of participants in the safety population E=Total number of protocol deviations x=Number of participants with a protocol deviation Percentages are based on the total number of participants in the safety population.
			

If multiple protocol deviations are reported for a participant, the participant may be counted in multiple rows corresponding to the different protocol deviation categories; however, they will be counted only once in the "Total" row. Therefore, the sum of participants may not add up to the "Total" row.

Programming Note: Print only the categories that have data

Table 7: Protocol Violations by Category – Safety Population

Protocol Violations Category	ROTAVIN N=XX x (%), E	ROTAVIN-M1 N=XX x (%), E	Total N=XX x (%), E
Total	x (%), E	x (%), E	x (%), E
Did not meet I / E criteria but enrolled	x (%), E	x (%), E	x (%), E
Dosed when withdrawal / discontinuation criteria were met	x (%), E	x (%), E	x (%), E
Incomplete vaccination: Replacement dose not administered in case of vomiting within 5 mins of administration	x (%), E	x (%), E	x (%), E
Informed Consent Not Taken	x (%), E	x (%), E	x (%), E
Incorrect Informed consent process: LAR not used when required	x (%), E	x (%), E	x (%), E
Damaged / Expired IP / Quarantined kit used without prior approval	x (%), E	x (%), E	x (%), E

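### The Enrolled population admits only eligible infants, and Safety, Full Analysis and Per Protocol all descend from it, which contradicts SAP Tables A2 and 7 on vaccinated infants who failed an eligibility criterion

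*SAP*

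**What the plan says.** The SAP's definition of Enrolled is: "The enrolled population is defined as all screened participants who provide informed consent and are eligible for study participation". The rest of the sentence sets aside randomization and treatment status, but not eligibility. Protocol 12.3.1 has the same wording.

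The other sets in SAP 7.1 are built on it:

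- FA: "all participants in the enrolled population who were randomized, received the first dose of the study vaccination", with at least one evaluable serum sample.
- PP: "The per-protocol population is defined as all participants in the FA population who correctly received both study vaccines per randomization", and without major deviations that could affect immunogenicity.
- Safety: "all participants in the enrolled population who received at least one dose of study vaccination and had any safety data available".

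Protocol 12.3.2 to 12.3.4 word the dose conditions slightly differently. For Safety the Protocol has "all participants in the enrolled population who received a study vaccination and had any safety data available". The dependence on Enrolled is the same in both documents. Both also say that the Safety population is used for all safety analyses.

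Two other parts of the SAP deal with infants who failed a criterion. Table A2, under Protocol Compliance, gives rows 1 to 22 to infants who were randomized despite failing one, and assigns each row a PP decision. Row 11, for example, is "Participant met exclusion criterion 7: History of congenital abdominal disorders, intussusception, abdominal surgery", and its decision is Include. The shell for Table 7, run on the Safety population, has the category "Did not meet I / E criteria but enrolled".

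**The concern.** The population definitions and the deviation rules cannot both be followed. If eligibility is a condition of Enrolled, Table A2 has nobody to include under its eligibility rows, and the Table 7 category is empty by construction. If Table A2 and Table 7 are followed, the definition of Enrolled is wrong. Two programmers could build different Safety and primary PP sets and each cite the SAP.

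The stakes are mainly in safety. Infants vaccinated despite prior intussusception, abdominal surgery, immune impairment or allergy to a vaccine component are among those whose events a reader would most want to see. Intussusception is a named safety endpoint. The listings would not recover the events: those for unsolicited AEs, SAEs and deaths (Listings 15, 17 and 18) are also restricted to the Safety population. Protocol 5.1.3 requires safety follow-up of infants in whom an exclusion criterion is detected during the dosing period. Where that finding shows the infant was never eligible, the literal definition leaves the follow-up data out of the analysis.

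**Working it through.** **1. Set membership, read literally**

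- Enrolled = consented and eligible.
- FA = Enrolled, randomized, Dose 1 received, at least one evaluable serum sample.
- PP = subset of FA.
- Safety = Enrolled, at least one dose, any safety data.

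Take an infant who was randomized and vaccinated but failed a criterion. Not being eligible, the infant is outside Enrolled, and therefore outside FA, PP and Safety.

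**2. Table A2, rows 1 to 22**

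| PP decision | Rows | Count |
|---|---|---|
| Include | 6, 7, 11, 13, 15, 16, 17, 18 | 8 |
| Case by case | 3, 4, 8, 10, 22 | 5 |
| Exclude | 1, 2, 5, 9, 12, 14, 19, 20, 21 | 9 |

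Check: 8 + 5 + 9 = 22. The Include rows correspond to exclusion criteria 2, 3, 7, 9, 11, 12, 13 and 14. Under the literal definition none of these 8 decisions can take effect, and the 5 reviews cannot admit anyone. The 9 Exclude rows give the same PP result either way. The conflict for PP therefore covers 8 + 5 = 13 rows. For Safety it covers all 22, since Table A2 decides PP only.

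**3. Other places that conflict with the literal definition**

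- Table 7: the category for failed criteria would always be zero in the Safety population. So would its category for consent not taken, because Enrolled also requires consent (the matching Table A2 row is 41).
- Table 1: percentages are based on randomized participants within Enrolled, so these infants would also leave the disposition denominators.
- Protocol Section 17 gives enrollment of infants who fail the criteria as an example of a protocol violation, so the case is foreseen.

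**4. Size**

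The plan's own power figure comes first. Inputs from SAP Section 5 are 250 versus 125 evaluable infants, SD 0.8 on the log10 scale, margin 0.5 and one-sided alpha 0.025. A true ratio of 1 is assumed.

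- Distance to the margin: log10(2) = 0.301.
- Standard error: 0.8 × √(1/250 + 1/125) = 0.0876.
- Noncentrality: 0.301 / 0.0876 = 3.44, with 373 degrees of freedom.
- Power from the noncentral t: 92.9%, which agrees with the stated 93%.

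The documents give no rate of eligibility violations. The fractions below are assumptions, applied equally to both arms:

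| Fraction removed | Evaluable infants | Power | Liquid-arm Safety set, from 550 |
|---|---|---|---|
| 0% | 250 vs 125 | 92.9% | 550 |
| 1% | 247.5 vs 123.75 | 92.6% | 544.5 |
| 2% | 245 vs 122.5 | 92.4% | 539 |
| 5% | 237.5 vs 118.75 | 91.6% | 522.5 |

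The stated 95% chance of seeing at least one reaction at a true incidence of 0.55% also reproduces: 1 − (1 − 0.0055)^550 = 95.2%. With 522 infants it is 94.4%.

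**The case against.** The best defence is that eligible means judged eligible at screening. Protocol 7.1 randomizes once eligibility has been ascertained. Protocol 15.8 closes enrollment when 825 infants have been screened and found eligible. SAP Table 1 has no category for infants randomized but not enrolled, and the footnote to Listing 1 gives non-vaccination as the reason enrolled infants are missing from Safety. Table 7 and Protocol Section 17 both treat infants who failed the criteria as enrolled. On this reading an infant later found to breach a criterion stays in Enrolled, FA and Safety, and Table A2 decides PP.

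This is plausible and probably what the authors meant. But the definition does not say it, and it does not clearly cover an infant randomized despite a criterion already known to have failed. It is a reason to correct the wording so that it states the intent.

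It is also fair that any loss would leave a trace. Table 8 and Listing 7 report exclusions from each population with reasons, and Listing 5 covers deviations and is not titled as restricted to Safety. SAE reporting (Protocol 9.10) and expedited committee review of intussusception (Protocol 9.12) do not depend on analysis populations. These show that an infant was excluded, or protect participants during the trial. They do not restore the events to the final safety tables.

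A reader might infer that the plan will in fact discard these infants' safety data, or that all 22 rows of Table A2 fail for PP. The documents support neither. The first follows only from the literal reading, against signs of the opposite intent. The second is wrong for the 9 Exclude rows.

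**Conclusion.** The contradiction is real and should be resolved, because it governs the Safety population and the primary PP set. As written, a vaccinated infant who failed a criterion belongs to no analysis population, while Table A2 keeps or may keep such an infant in PP under 13 of 22 rows and Table 7 counts such infants in Safety.

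The number of infants affected is unknown and may be zero. Under the assumed fractions of 1% to 5%, non-inferiority power falls by at most 1.3 percentage points (92.9% to 91.6%), so a reader should not infer a threat to the primary test's power. What matters is whose events are counted. Even one serious event in a vaccinated infant who failed a criterion would be absent from the SAE tables under the literal rule.

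**What to change.** Before database lock, take eligibility out of the population chain in SAP 7.1 and Protocol 12.3:

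- **Safety:** all participants who received at least one dose of study vaccine and have any safety data, regardless of eligibility.
- **FA:** all randomized participants who received Dose 1 and have at least one evaluable serum sample, regardless of eligibility.
- **PP:** a subset of FA as now, with eligibility violations acting only through Table A2.
- **Enrolled:** if kept for disposition, define it without the eligibility condition, so that the Table 1 denominators include every randomized infant.
- **Consent:** state explicitly how the consent condition applies to Safety, so that Table A2 row 41 and the Table 7 category for consent not taken agree with the definition.

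This is a wording change and needs no new data. The Protocol text would go through the amendment route in Protocol Section 16.
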